Our emergency department sees an average of 150 cases of DKA per year and our center is involved in multiple clinical trials studying DKA management in children. Further, members of our group have been influential in developing a hospital-wide DKA protocol that is utilized both in the emergency department as well as in the inpatient setting to establish standardized and safe clinical care.

Glargine administration early in DKA management has been studied by our colleagues at University of Colorado Hospital in adults (with direct involvement from our co-mentor [name]). This group found that early administration of glargine in DKA resulted in a decreased rate of rebound hyperglycemia (33.3% versus 93.5%, $p < 0.001$ (14)). This data cannot be directly translated into the care of children in DKA, however, given the increased risk of complications in children such as cerebral edema and adverse events related to severe hypoglycemia. Therefore, without good pediatric data, the timing of glargine administration during the management DKA in children is left up to the discretion of the Diabetes Care Team and is, therefore, variable. Over the past 3-4 years, giving early glargine in DKA in children appears, anecdotally, to work well in the transition to subcutaneous insulin. It is viewed by many Diabetes providers to be a practical method and many are comfortable with this technique.

No data looking exclusively in children exist on whether early glargine administration in DKA management results in reduced rates of rebound hyperglycemia, is protective against recurrent ketogenesis, or how this relates to the risk of hypoglycemia. Further, no data exist on use of CGM technology in children treated for DKA. This detailed information will provide novel knowledge of blood glucose response both during treatment of DKA, and in the immediate phase following resolution of DKA, and help broaden our understanding of type 1 diabetes. CGM use in the hospital may also reduce the risk of hypoglycemic events and therefore improve patient safety.

IV. Research Methods:

A. Outcome Measure(s):

Primary outcome: Rate of rebound hyperglycemia within 12 hours (or until time to hospital discharge if less than 12 hours) after discontinuation of IV insulin on glucometer.

- Percent of patients with blood glucose > 180 mg/dL.
- Median blood glucose.

Secondary outcomes:

1. Rate of rebound hyperglycemia (as described in primary outcome) on CGM.

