 - Percent of patients with blood glucose > 180 mg/dL.
 - Median blood glucose.
 - Percent of time with blood glucose > 180 mg/dL.
2. Rate of recurrent ketogenesis (serum beta-hydroxybutyrate \geq 1.5 mmol/L) within 12 hours (or until time to hospital discharge if less than 12 hours) after discontinuation of IV insulin.
 - Rate of late-recurrent ketogenesis (serum beta-hydroxybutyrate \geq 1.5 mmol/L) 12-18 hours after discontinuation of IV insulin for participants who remain hospitalized for over 24 hours.
3. Frequency of hypoglycemic events while on IV insulin (and within 12 hours after discontinuation of IV insulin) on glucometer or CGM.
 - Glucometer: percent of patients with blood glucose < 70 mg/dL (+/- 2 hours of an "index" hypoglycemic event).
 - CGM: % of time with blood glucose < 70 mg/dL.
4. Rate of blood glucose decrease while on IV insulin on glucometer and CGM within the following time points: 0-2 hours, 2-4 hours, 4-6 hours, >6 hours.
5. Number of participants who needed a decrease in their IV insulin rate (secondary to hypoglycemia).
6. Feasibility of using CGM as a tool for glucose monitoring in DKA.
 - Percent of CGM failures during treatment of DKA.
 - Correlation of CGM to POC glucose monitoring during DKA.

B. Description of Population to be Enrolled:

Eligible patients will be enrolled from Children's Hospital Colorado Emergency Department; a large tertiary care ED and level I trauma center in Aurora, Colorado. These will be patients with either a known diagnosis of T1D presenting in DKA or a new diagnosis of T1D presenting in DKA (see inclusion criteria). Patients will be enrolled either by the PI or a member of the study team (who will be available between the hours of 8:00 am and midnight). Depending on study team member availability, and due to the variability of time of presentation to the ED, patients who present outside of these hours may not be able to be enrolled into the study.

In this study we aim to approach 100 participants, both males and females aged 6-17.99 years, who present in DKA. Assuming 80% of participants approached will be eligible to participate and 60% of eligible subjects will consent to participate, this provides at least 48 subjects, which is needed for 80% power to detect an absolute difference of 40% difference in the rate of rebound hyperglycemia.

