3. Use of medications that are known to affect blood glucose levels (oral glucocorticoids, Metformin, SGLT2 inhibitors, GLP-1 receptor agonists, DPP-4 inhibitors, TZDs, sulfonylureas, vasopressors, etc.).
4. Participants who have begun DKA treatment prior to being approached for enrollment and have received more than 6 hours of IV insulin therapy.
5. Participants with established T1D who have received a dose of long-acting insulin within the following time frames:
 - a. Tresiba® (Degludec): within the past 20 hours at time of enrollment.
 - b. Lantus® (Glargine): within the past 12 hours at time of enrollment.
 - c. Levemir® (Detemir): within the past 6 hours at time of enrollment.
6. Participants who are known to be pregnant.
7. Participants who have a known diagnosis of type 2 diabetes (autoantibody negative, use of oral hypoglycemic medications).
8. Participants for whom the treating physicians feel a specific insulin regimen is necessary such that patient safety or well-being could be compromised by enrollment into the study.

C. Study Design and Research Methods

C.1. Recruitment/Enrollment:

Eligible patients will be enrolled from Children's Hospital Colorado Emergency Department after determination of DKA status. Informed consent and assent will be obtained following standard COMIRB approved methods by the PI and/or members of the research team.

Participants completing the informed consent/assent process will be cataloged in a secure (password-protected) database. Data collected will include: Protected Health Information (PHI) including name, date of birth, medical record number, sex, and race/ethnicity. Participants will then be assigned a study number and PHI de-identified.

We have discussed this research protocol with the Emergency Department Research Team and they have determined that this is a suitable study. Further, our department has a long history of collaboration with our Emergency Department.

C.2. Study Protocol:

Participants will be randomized and treated according to the study protocol outlined in Figure 1.

[figure not shown]

Figure 1: Outline of study protocol. BMP = basic metabolic panel; VBG = venous blood gas; UA = urinalysis; BHB = beta-hydroxybutyrate; DKA = diabetic ketoacidosis; CGM = continuous glucose monitor; NS = normal saline; IV = intravenous; IVF = intravenous fluids; POC = point-of-care; HbA1c = hemoglobin A1c; K = potassium; HCO3 = serum bicarbonate; PI = Primary Investigator.

C. 2.1 During DKA treatment:

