- Upon diagnosis of DKA patients will begin rehydration with standard fluid therapy using an initial IV bolus of 10mL/kg of 0.9% saline.
- Fluid boluses may be repeated at the discretion of the treating physician to restore hemodynamic instability.
- During initial therapy, study personnel will obtain informed consent. .
- Participant Data: basic information such as name, date of birth, race/ethnicity, and diagnosis will be collected.
- Randomization:
 - We will use a blocked, stratified randomization scheme to allocate participants 1:1 to treatment groups. Randomization will be stratified within new onset and existing T1D patients to ensure balance across treatment groups.
 - Ideally, randomization will occur during the initial fluid bolus, however, if this is not possible then the patient will be treated with the standard DKA protocol for this study site until consent is completed, but not beyond the time frame outlined in the exclusion criteria.
 - Participants will be randomized into one of two groups:
 - 1. Early glargine, study group (N ~ 25):**
 - a. Administer glargine SQ x 1 when pH \geq 7.10.
 - b. Primary investigator and/or on-call co-investigator to determine glargine dose:
 - i. New onset T1D: 0.3 units/kg
 - ii. Established T1D: use home total daily dose (TDD) of long-acting insulin (or TDD of basal if on an insulin pump), converted to glargine equivalents.
 - 2. Standard-of-care, control group (N ~ 25):**
 - a. Administer glargine SQ x 1 at time of correction of acidosis (venous pH \geq 7.3 and serum bicarbonate \geq 18 or BHB \leq 1) and discontinuation of IV insulin.
 - b. Primary investigator and/or on-call co-investigator to determine glargine dose as described above.
- After initial fluid bolus(es), standard insulin therapy begins with a continuous infusion of IV regular insulin at a rate of 0.1 units/kg/hr.
- Ongoing rehydration is established using IV fluids with $\frac{3}{4}$ normal saline at a standard rate of 1.5 x maintenance unless this is determined to be harmful by the primary attending physician.
- Potassium replacement is provided using IV fluids containing potassium acetate and potassium phosphate.
- When serum glucose concentration declines below 250 mg/dL, dextrose (5-12.5%) is added to the IV fluids to maintain serum glucose between 100 mg/dL and 200 mg/dL.

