- Participants will return the CGM sensor to study personnel after approximately 1 week (see section C.2.3 below).

C.2.2. Upon resolution of DKA:

- When venous pH ≥ 7.3 and serum bicarbonate ≥ 18 mmol/L (or BHB < 1.0 mmol/L) and participant is awake and alert, he/she will be transitioned to subcutaneous insulin:
 - Discontinuation of IV insulin.
 - Initial subcutaneous dosing:

- Glargine: 0.3 units/kg SQ x 1 for new onset T1D (or home glargine equivalent dose for established T1D) – if not already given as part of the Early Glargine/study group (see section C. 2.1 for dosing).
- Lispro: 0.2-0.6 units/kg/day, administered using a standard Multiple Daily Injection (MDI) regimen: before meals or as needed for hyperglycemia (but not more often than every 4 hours).
- The on-call physician can override the above dosing based on clinical judgment.
- **Insulin pump:** Participants with established T1D who are managed with an insulin pump at baseline will have the option to either:
 1. NOT reconnect or use their insulin pump for 24 hours after the protocol glargine dose was administered and will receive standard MDI therapy during that time with dosing determined by the inpatient diabetes team or study personnel. They can resume full home insulin pump use after 24 hours following glargine administration.
 2. Reconnect their home insulin pump to use for BOLUSING ONLY with meals and snacks and will not use their basal rate (set a temporary basal rate of 0%) for 24 hours after the glargine dose was administered. They can resume full home insulin pump use after 24 hours following glargine administration.

Laboratory monitoring upon resolution of DKA:

- Blood glucose concentration obtained before meals, at bedtime, and at 0200 using point-of-care glucometer.
- Serum BHB obtained every 6 hours until ≤ 1.0 mmol/L or at any time if blood glucose on glucometer is > 300 mg/dL for two consecutive measurements.
- Participants who remain hospitalized over 24 hours will have a BHB drawn at 12-18 hours after discontinuation of IV insulin to assess for late-recurrent ketosis.

Table 1: Summary of laboratory monitoring:

| Data: | During DKA | Upon resolution of DKA |
|---------------------|--|--|
| POC glucose (mg/dL) | At presentation and hourly | Before meals, at bedtime, at 0200 |
| BMP | At presentation and approx. every 2-4 hours | As needed |
| HbA1c (%) | At presentation | |
| VBG | At presentation and approx. every 2-4 hours | As needed |

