1. **Participant Data:** Collection of patient data always holds a small risk of data breach. All research staff will be trained in good clinical practice and HIPAA. Any paper PHI will be stored in a locked study office and all electronic data records maintained by the study investigator for analysis will be password protected. Participants will be assigned a study number and de-identified datasets using only the study number will be used for analysis. This study number will be linked to the participant's PHI through a table accessible only to the PI, co-investigators, and research staff. Any other electronic or paper records which could be linked to the participant record or medical chart will be deleted or destroyed. PHI will not be connected to the data used in any manuscript or publication.
2. **General:** An experienced Diabetes Team (Barbara Davis Center) is routinely consulted on all patients with type 1 diabetes who present to Children's Hospital Colorado and is closely involved in their care throughout the hospitalization with regard to DKA management, blood glucose monitoring, and subcutaneous insulin dosing. The primary Diabetes Team routinely dictates when glargine is administered and at what dose. See "Subcutaneous insulin injection" section for additional details.
3. **Hypoglycemia:** blood glucose levels will be monitored closely throughout the hospitalization and hypoglycemic events will be treated per standard hospital hypoglycemia protocol. It is routine to monitor blood glucose hourly while on IV insulin and at least 4 times per day once off IV insulin. Once discharged from the hospital, participants will be instructed to check blood glucose levels at least 4 times per day and to call the Barbara Davis Center with any hypoglycemia issues or concerns.
4. **Venipuncture to draw blood for laboratory evaluation:** Venipuncture will be performed by clinical staff with experience with venipuncture to reduce the risk of pain and/or infection. Gloves will be worn and the area of skin cleaned per hospital policy to prevent risk of infection.

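### The recent long-acting insulin exclusion covers established T1D only, so a new-onset child already given glargine in this episode can be randomized to control

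*Combined protocol and SAP*

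**What the plan says.** **Eligibility (section IV.B).** Exclusion 5 applies to "Participants with established T1D who have received a dose of long-acting insulin within the following time frames", and the glargine window is "within the past 12 hours at time of enrollment" (20 hours for degludec, 6 for detemir). Exclusion 4 removes children who started DKA treatment before being approached and "have received more than 6 hours of IV insulin therapy"; it does not mention subcutaneous insulin. Exclusion 3 names glucose-altering drugs, none of them insulin. New-onset children are eligible and form one of the two randomization strata.

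**Care before randomization (section IV.C.2.1).** Randomization is meant to happen during the first fluid bolus, but "if this is not possible then the patient will be treated with the standard DKA protocol for this study site until consent is completed", within the limit set by the exclusions. Study staff are those "who will be available between the hours of 8:00 am and midnight" (section IV.B).

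**Glargine in usual care.** Section III says "the timing of glargine administration during the management DKA in children is left up to the discretion of the Diabetes Care Team", calls the practice variable, and describes favorable experience with early dosing over 3-4 years. Section IV.D adds: "The primary Diabetes Team routinely dictates when glargine is administered and at what dose".

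**Control-arm dose.** Section IV.C.2.1 gives controls one dose at correction of acidosis. Section IV.C.2.2 waives the dose at resolution only "if not already given as part of the Early Glargine/study group".

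**The concern.** Section IV.D states that the arms differ only in when glargine is given. A control child who had it before enrollment has no timing difference from the early arm, yet counts as eligible and on protocol. Analysis as randomized would not reveal this, nor would the logistic model, which adjusts for BMI, sex, age and diabetes status. The data items listed in section IV.D do not name the time of an earlier long-acting dose. The measured difference would shrink without a trace.

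The strata are also handled unequally: an established-T1D child with the same glargine history is kept out. Finally, the waiver in section IV.C.2.2 is tied to the study arm, so read literally it leaves a pre-treated control due another dose. That would also bear on the hypoglycemia comparison in Aim 3.

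**Working it through.** **1. Is the route open on the text?**

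| Step | Text | Closed for new-onset? |
|---|---|---|
| Recent long-acting insulin | Exclusion 5 | No, established T1D only |
| Prior treatment | Exclusion 4 | No, caps IV insulin only |
| Other drugs | Exclusion 3 | No, names no insulin |
| Care until consent | IV.C.2.1 | No, site protocol continues |
| Glargine timing in usual care | III, IV.D | No, Diabetes Team decides |
| Treating physician's judgment | Exclusion 8 | Only by discretion; prior glargine not mentioned |

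On timing, a child who starts IV insulin at 2 am or later is still within 6 hours when staff become available at 8 am. Section IV.B warns that children presenting outside staffed hours may be missed, so this is possible rather than routine.

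**2. Would the existing window catch the dose if it applied?** Glargine given during at most 6 hours of IV insulin is at most 6 hours old at enrollment, inside the 12-hour window. Removing the restriction to established T1D would therefore catch it.

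**3. The plan's own sample size.** Inputs from section VII: early-arm rate 0.30, difference 0.40 (so control rate 0.70), alpha 0.05 (two-sided reproduces the table), power 80%, 1:1 allocation.

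n per arm = [1.960 × √(2 × 0.5 × 0.5) + 0.842 × √(0.21 + 0.21)]² / 0.40² = 23.3, rounded up to 24, total 48. This matches the power table, and the same formula reproduces the other four columns (186, 122, 84, 30).

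**4. Effect per affected control.** Assumption, not in the documents: a pre-treated control has the early-arm rate of 0.30. With k such children among n controls, the difference is 40 × (1 − k/n) points, a loss of 40/24 = 1.67 points per child at n = 24. Exact power is for the uncorrected chi-squared test, with k controls at 0.30 and the rest at 0.70.

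| k | Difference, 24 per arm | Formula power, 24 | Exact power, 24 | Exact power, 25 |
|---|---|---|---|---|
| 0 | 40.0 | 81.2% | 83.6% | 85.9% |
| 1 | 38.3 | 77.5% | 80.4% | 83.1% |
| 2 | 36.7 | 73.4% | 76.8% | 79.9% |
| 3 | 35.0 | 69.1% | 72.9% | 76.4% |

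Within the new-onset stratum the dilution is larger. If it holds 12 of 24 controls (assumption), the difference there is 36.7, 33.3 and 30.0 points for k = 1, 2 and 3.

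**5. If the dose were repeated.** The new-onset dose is 0.3 units/kg. If the first dose was the same (assumption), the total is 0.3 + 0.3 = 0.6 units/kg. With the 20-24 hour action stated in section IV.D, doses 8 hours apart (an illustrative gap) overlap for 20 − 8 = 12 to 24 − 8 = 16 hours.

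**The case against.** The strongest reply is that the route is narrow. Section I describes standard care as glargine once the acidosis has fully resolved, so a child treated that way before consent would rarely have had it within 6 hours of IV insulin. The hospital protocol is linked rather than reproduced, and Figure 1 is not shown; either might hold glargine until resolution. Randomization is intended before IV insulin starts. Exclusion 8 gives the treating physician a way to keep a child out. All of this stands as a reason to expect few cases. It does not close the gap, because section III says timing in children here is discretionary and variable.

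A reader might infer from the waiver wording that pre-treated controls will receive two full doses. The documents do not support that. Both arms specify a single dose, the investigator or on-call co-investigator sets it, the on-call physician may override it, and the Diabetes Team follows the child throughout. A duplicate would require several clinicians to miss a charted dose. Nor is overlap in itself new to this design: an established-T1D child may enroll just over 12 hours after glargine, when an immediate further dose would overlap by about 20 − 12 = 8 to 24 − 12 = 12 hours. What remains is that the waiver is worded too narrowly.

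A reader might also infer that the trial loses its power. With no count of pre-consent glargine in the documents, that cannot be said.

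**Conclusion.** The gap is real and lies in a stated rule: a new-onset child who has already had early glargine is eligible and can be randomized to control, whereas an established-T1D child with the same history is excluded. Each such control costs about 1.7 points of the planned 40-point difference at 24 per arm. One leaves power at about 80% (80.4% exact; 77.5% by the plan's own formula), and three would bring exact power to 72.9%. These figures assume the 30% early-arm rate for the affected child. Frequency is not given and is probably low. The case for change therefore rests on a clean timing contrast and consistent eligibility, not on a demonstrated loss of power or an expected double dose.

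**What to change.** - In exclusion 5, delete the words limiting it to established T1D, so that it covers any participant with a long-acting dose inside the stated windows, and say that this includes a dose given during the current DKA episode.
- As a safety backstop, reword the waiver in section IV.C.2.2 so that the resolution dose is omitted whenever glargine has already been given in this episode, whatever the reason.
- Record the time of any long-acting dose given before randomization, and report it by arm.

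Do not add a rule withholding long-acting insulin before consent; that would have the study restrict clinical care for children not yet enrolled.

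The cost is a few words in two places and one data field, with no extra tests and N still 48-50. A few new-onset children become ineligible (number not given); section IV.B already allows for 20% of those approached being ineligible.
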